4. POPULATIONS (ANALYSIS SETS) FOR ANALYSIS

The following sets will be used for analyses.

Table 4: Analysis sets

Analysis Sets	Description	
Enrolled	All participants who signed the ICF	
Randomized	All participants who were randomized in the study	
Full Analysis Set (FAS)	All randomized participants who received at least 1	
	(partial or complete) dose of study intervention	
Rescue Analysis Set	All participants in the FAS who met rescue criteria (as	
	determined by the IWRS) and received at least one	
	(partial or complete) dose of study intervention at or	
	after Week 16. This includes both participants	
	randomized to placebo and participants randomized to	
	one of the guselkumab groups who were assigned sham	
	rescue treatment.	

Analysis Sets	Description	
Week 12 Clinical Responder Analysis Set	All participants in the FAS who met Clinical Response	
	Criteria at Week 12 as defined in Section 5.4.1.1 and	
	received at least 1 (partial or complete) dose of study	
	intervention after Week 12	
Safety	All randomized participants who received at least 1	
	(partial or complete) dose of study intervention	
Pharmacokinetics (PK) Analysis Set	All participants who received at least 1 (partial or	
	complete) dose of guselkumab and have at least 1 valid	
	blood sample drawn for PK analysis after their first dose	
	of guselkumab	
Immunogenicity Analysis Set	All participants who received at least 1 (partial or	
	complete) dose of guselkumab and have appropriate	
	serum samples for detection of antibodies to	
	guselkumab after their first dose of guselkumab	

5. STATISTICAL ANALYSES

5.1. General Considerations

Descriptive statistics (e.g., mean, median, SD, IQ range, minimum, and maximum) will be used to summarize continuous variables. Counts and percentages will be used to summarize categorical variables. Graphical data displays (e.g., line plots) may also be used to summarize data. This applies to demographic and baseline characteristics given in Appendix 3.

Analyses suitable for categorical data (e.g., chi-square tests, CMH chi-square tests, or logistic regression, as appropriate) will be used to compare the proportions of participants achieving selected endpoints (e.g., clinical response). In cases of rare events, the Fisher's exact test will be used for treatment comparisons. Continuous response parameters measured at more than one postbaseline visit will be compared using a MMRM model (unless otherwise specified). If the normality assumption is in question, an appropriate transformation may be implemented before fitting the MMRM model. Continuous response parameters measured at only one post-baseline visit will be compared using an ANOVA or ANCOVA, unless otherwise specified. In cases of small sample size, t-test will be used for treatment comparisons.

The overall Type I error rate over primary and secondary endpoints will be controlled at the significance level of 0.05 (2-sided).

Unless otherwise specified, the analysis of endpoints related to the endoscopy subscore, including the modified Mayo score, will be based on the final reported Mayo endoscopy subscore (Section 5.3.1).

Baseline assessment

Baseline assessment is defined as the last available assessment collected prior to or on the day of the first administration of study intervention, unless otherwise specified.

Study day

Study day 1 (Day I) is the date of the first administration of study intervention in the study.

The *study day* for a post-baseline scheduled or unscheduled visit is defined as:

Study day = (date of visit) - (date of first administration of study intervention) + 1.

The study day for a scheduled or unscheduled visit before Baseline is defined as:

Study day = (date of visit) – (date of first administration of study intervention).

There is no "Study Day 0".

Unscheduled visits

All data collected at unscheduled visits will not be used in "by visit" tabulation or graphs for safety analyses but will be included for analyses based on all post-baseline assessments, such as safety narratives and summary of maximum increase/decrease from Baseline for laboratory data. Unscheduled visits for efficacy assessments will be slotted to scheduled visits (see Section 5.1.1). All data collected at scheduled and unscheduled visits will be included in listings.

Combined guselkumab groups

Both guselkumab groups will receive identical study intervention for Week 0, 4, and 8. For analyses of timepoints up to Week 12, these groups will therefore be combined, and the combined group will be referred to as combined guselkumab. Note that for analyses of courses over time which include a period beyond Week 12, the two guselkumab groups may be analyzed separately.

5.1.1. Visit Windows

Unless otherwise specified, actual scheduled visits will be used for over time summaries and listings with no visit windows applied. Early Discontinuation (ED) and unscheduled efficacy visits will be slotted to scheduled visits according to the following mapping rules:

- 1. Assign a visit number to ED or unscheduled visit based on the visit day according to Table 6.1 and Table 6.2.
- 2. If the ED or unscheduled visit falls in the window of a scheduled visit for which there is no data recorded, assign the scheduled visit number to the ED or unscheduled visit. If there is data recorded for the scheduled visit, those data will be used in lieu of the ED or unscheduled visit data.

Table 5.1: Visit windows for analysis of Mayo score, endoscopy score and histology assessment

Parameter	Time interval (label on output)	Time interval (Day)*	Target time point (Day)
Partial Mayo Score	Week 4	16-43	29
	Week 8	44-71	57
	Week 12	72-99	85
	Week 16	100-127	113
	Week 20	128-155	141
	Week 24	156-183	169
	Week 28	184-211	197
	Week 32	212-239	225
	Week 36	240-267	253
	Week 40	268-295	281

CONFIDENTIAL – FOIA Exemptions Apply in U.S.

11

	Week 44	296-323	309
	Week 48	324-351	337
Endoscopy subscore, full			
Mayo score including	Week 12	57-113	85
modified Mayo score			
	Week 24	141-197	169
	Week 48	309-365	337
Histology assessment	Week 12	57-113	85
	Week 48	309-365	337

^{*} Relative to Study Day 1

Table 6.2: Visit windows for analysis of IBDQ, PROMIS-29, UC-PRO/SS, fecal calprotectin, CRP

D	Time interval	Time interval	Target time point
Parameter	(label on output)	(Day)*	(Day)
IBDQ, PROMIS-29	Week 12	57-113	85
	Week 24	141-197	169
	Week 48	309-365	337
UC-PRO/SS	Week 4	16-43	29
	Week 8	44-71	57
	Week 12	72-99	85
	Week 16	100-127	113
	Week 20	128-155	141
	Week 24	156-183	169
	Week 28	184-211	197
	Week 32	212-239	225
	Week 36	240-267	253
	Week 40	268-295	281
	Week 44	296-323	309
	Week 48	324-351	337
Fecal calprotectin	Week 4	16-56	29
•	Week 12	57-113	85
	Week 24	141-197	169
	Week 48	309-365	337
CRP	Week 4	16-43	29
	Week 8	44-71	57
	Week 12	72-99	85
	Week 16	100-127	113
	Week 20	128-155	141
	Week 24	156-196	169
	Week 32	197-253	225
	Week 48	309-365	337

^{*} Relative to Study Day 1

5.2. Participant Dispositions

The number of participants in the following disposition categories through Week 12, Week 24, and Week 48 will be summarized by treatment group and overall based on the Full Analysis Set, the Rescue Analysis Set and the Week 12 Clinical Responder Analysis Set:

- Participants who received study intervention
- Participants who discontinued study intervention
 - Reasons for discontinuation of study intervention
- Participants who terminated study prematurely
 - Reasons for termination of study

Listings of participants will be provided for the following categories:

- All randomized participants
- Participants who discontinued study intervention
- Participants who terminated study prematurely
- Listing of participants with major protocol deviations as given in Appendix 4.

Listings will identify the visits completed and when the study intervention was discontinued or the study was terminated. Further listings regarding intervention compliance are described in Appendix 7.

In addition, the number and percentage of participants who met rescue criteria (according to the IWRS) will be summarized for the full analysis set.

[figure not shown]
5.3. Primary Endpoint Analysis

5.3.1. Definition of Endpoint

[figure not shown]
The primary endpoint is clinical remission at Week 12.

Clinical remission is defined as a stool frequency subscore of 0 or 1 and not increased from baseline, a rectal bleeding subscore of 0, and an endoscopy subscore of 0 or 1 with no friability present on the endoscopy.

The above definition is based on Mayo score components as described below.

5.3.2. **Estimands**

An estimand is a precise definition of the primary targeted intervention effect defined by the following 5 attributes: study intervention by Week 12, population, variable (endpoint), intercurrent events (ICEs) and corresponding strategies, and population-level summary.

Primary Trial Objective: To evaluate the efficacy of guselkumab SC at Week 12 compared with placebo SC.

Estimand Scientific Question of Interest: What difference in proportions of patients considered to experience benefit from treatment by Week 12 (according to the responder criteria for clinical remission used in the estimand variable definition) can be expected under the assignment to either guselkumab or placebo?

5.3.2.1. **Primary Estimand (Estimand 1)**

The primary estimand (i.e., a precise definition of the primary targeted treatment effect) is defined by the following 5 attributes:

i) Treatment by Week 12:

Experimental: Combined guselkumab induction dose group (i.e., both guselkumab groups who received at Weeks 0, 4, and 8; see Section 1.2)

CONFIDENTIAL – FOIA Exemptions Apply in U.S.

Control: Placebo SC q4w (Weeks 0, 4, 8)

- **ii) Population**: Participants with moderately to severely active ulcerative colitis as reflected in the inclusion/exclusion criteria.
- **iii)** Variable (Endpoint): A binary response variable (response/nonresponse) where response is defined as achieving a stool frequency subscore of 0 or 1 and not increased from baseline, a rectal bleeding subscore of 0, and an endoscopy subscore of 0 or 1 with no friability present on the endoscopy at Week 12 and none of the ICEs in categories 1 to 4 and 6 outlined in Table 6 has occurred prior to the Week 12 visit.
- iv) Intercurrent Events and Corresponding Strategies: ICEs and the corresponding analysis strategies are defined in Table 6.

Table 6: Intercurrent Events and Respective Analysis Strategies

ICE	Analysis strategy for ICE
1. An ostomy or colectomy (partial or total)	Composite strategy: Occurrence of these ICEs will be
2. A prohibited change in medications for UC (as	treated as an unfavorable outcome
defined in Appendix 14)	
3. Discontinuation from study intervention due to lack	
of efficacy or an adverse event (AE) of UC worsening	
4. Meeting rescue criteria (as determined by the IWRS)	
(Note: Since rescue criteria are assessed at Week 16	
for all participants, this ICE is not applicable for the	
primary endpoint or any of the key secondary Week 12	
endpoints)	
5. Discontinuation of study intervention due to	Treatment policy strategy: Observed values will be
COVID-19 related reasons (excluding COVID-19	used if available
infection) or regional crisis	
6. Discontinuation of study intervention due to reasons	Composite strategy: Occurrence of these ICEs will be
other than ICEs 3 or 5 as described above	treated as an unfavorable outcome

The composite strategy assesses the treatment effect not only based on the variable measurements, but also on ICEs. This estimand acknowledges that having an ICE in categories 1-4 and 6 is an unfavorable outcome. For participants experiencing an ICE in category 5, the treatment policy strategy considers the occurrence of ICE category 5 as irrelevant in defining the treatment effect.

v) Population-level summary: Difference in proportions of participants who achieved the binary response at Week 12 as defined in the variable attribute above between the combined guselkumab group and the placebo group.

5.3.2.2. Supplementary Estimands for the Primary Endpoint

The supplementary estimands are defined to support the primary endpoint.

5.3.2.2.1. Treatment policy for discontinuations (Estimand 2)

The supplementary estimand (Estimand 2) handles all treatment discontinuation ICEs, i.e. ICEs 3, 5 and 6 in Table 6, by the treatment policy strategy. ICEs 1 2 and 4 continue to be handled by the composite strategy. This leads to the following variable definition:

iii) Variable (Endpoint): A binary response variable (response/nonresponse) where response is defined as achieving a stool frequency subscore of 0 or 1 and not increased from baseline, a rectal bleeding subscore of 0, and an endoscopy subscore of 0 or 1 with no friability present on the endoscopy at Week 12 and none of the ICEs in categories 1, 2 and 4 outlined in Table 6 has occurred prior to the Week 12 visit.

5.3.2.2.2. Alternative Mayo Score Calculation (Estimand 3)

This supplementary estimand (Estimand 3) follows the primary estimand in all attributes. The eligible days to be used for the Mayo scoring for this estimand are all available days among the seven days prior to each visit, excluding programmatically the following two days:

- 1. The day(s) of a procedure (including colonoscopy or sigmoidoscopy)
- 2. The day preceding such a procedure.

5.3.2.2.3. Participants with Non-missing Stool Frequency subscore at Baseline (Estimand 4)

This estimands shares all properties of the primary estimand as given in Section 5.3.2.1 with the exception of the population, which is defined as follows for this estimand:

ii) Population: Participants with moderately to severely active ulcerative colitis as reflected in the inclusion/exclusion criteria and with a stool frequency subscore recorded at baseline.

5.3.3. Analysis Methods

5.3.3.1. Main Estimator (Analysis) for the Primary Estimand

The analysis of the primary estimand will be based on the FAS, which includes all randomized participants who received at least 1 dose (partial or complete) of study intervention. Participants will be analyzed according to the intervention group to which they were randomized regardless of the study intervention they actually received.

Regarding the ICE strategies, for the treatment policy strategy, the associated ICE will be ignored, and any data observed after the associated ICE will be used for analysis. After accounting for the ICE strategies, participants who are missing any or all of the three subscores that comprise the primary endpoint at Week 12 will be considered not to be in clinical remission at Week 12. Participants who are missing the stool frequency subscore at baseline will be considered not to be in clinical remission at Week 12.

Summaries of the proportion of participants in clinical remission at Week 12 by treatment group along with the adjusted treatment difference between the combined guselkumab SC induction group and the placebo group, as well as the associated 95% confidence interval will be presented. Comparison against placebo will be performed in terms of the common (overall) risk difference for multiway 2x2 tables at a two-sided significance level of 0.05. Specifically, the adjusted treatment difference, 95% confidence interval, and p-value will be in terms of the common risk difference by use of Mantel-Haenszel stratum weights and the Sato variance estimator;

stratification is by ADT-IR status (Yes/No), and Mayo endoscopy subscore at baseline (moderate [2] or severe [3]).

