9.4.2.2. Estimator for the Primary Endpoint

The analysis of the primary endpoint will be based on the Full Analysis Set. Participants will be analyzed according to the treatment group to which they were randomized regardless of the treatment they received.

After accounting for the ICE strategies, any participants who are missing any or all of the 3 that comprise the primary endpoint at Week 12 will be considered not to be in clinical remission at Week 12 (ie, nonresponder imputation).

Summaries of the proportion of participants in clinical remission at Week 12 will be presented by treatment group. The common risk difference and the associated 95% confidence interval between the combined guselkumab SC induction group and the placebo group will be computed by use of Mantel-Haenszel stratum weights and the Sato variance estimator. The primary endpoint will be tested by a two-sided Mantel-Haenszel test for the common risk difference. Stratification will be by the ADT-IR status (Yes/No), and CCl at baseline (moderate [2] or severe [3]) as obtained during central review of the video endoscopy. The study will be considered successful if the test for the primary endpoint is positive. While a multiplicity-controlled testing procedure will be implemented to control for the Type I error rate at the 0.05 significance level (2-sided) across the primary and secondary endpoints, the primary endpoint will be tested at full significance level. Only if this test is significant, secondary endpoints will be tested in a confirmatory manner.

To evaluate the robustness of the primary analysis results, sensitivity analyses using alternative missing data handling rules may be performed and supplementary estimands will be evaluated; these analyses will be described in the SAP. In particular, this includes the use of the treatment policy strategy for ICEs 3, 4, and 5 in Table 8 while continuing to use the composite strategy for ICEs 1 and 2.

In addition, subgroup analyses of the primary endpoint will be performed based on demographic and baseline disease characteristics, and baseline use and history of use of UC medications (including ADT-IR status).

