1.2. Study Design

This is a randomized, double-blind, placebo-controlled, parallel-group, multicenter study to evaluate the efficacy and safety of guselkumab SC induction therapy in adult participants with moderately to severely active UC defined as a modified Mayo score of 5 to 9, inclusive, Mayo rectal bleeding subscore ≥ 1 and a Mayo endoscopy subscore ≥ 2 . Participants must have demonstrated an inadequate response to or intolerance of conventional (i.e., 6-mercaptopurine (6-MP), azathioprine (AZA), or corticosteroids) or advanced therapy (ADT; i.e., tumor necrosis factor (TNF) α antagonists, vedolizumab, ozanimod, or approved Janus kinase (JAK) inhibitors). An overview over the study design is given in Figure 1.

A target of 399 participants will be enrolled in this study with 133 participants planned per intervention group. Participants who had an inadequate response to or intolerance of advanced therapy (ADT-IR) will comprise a minimum of approximately 40% and a maximum of approximately 50% of the population. Consented participants will be screened for study eligibility within 8 weeks of the Week 0 visit. Eligible participants will be randomized in a 1:1:1 ratio to the following intervention groups:

- Guselkumab CCI at Weeks 0, 4, and 8 followed by guselkumab 200 mg SC q4w through Week 24
- Guselkumab CCl at Weeks 0, 4, and 8 followed by guselkumab 100 mg SC q8w through Week 24
- Placebo SC q4w from Week 0 through Week 24

Participants will be allocated to an intervention group using permuted block randomization stratified by ADT-IR status (Yes/No) and Mayo endoscopy subscore at baseline (moderate [2] or severe [3]).

At weeks 12 and 16, all participants will be evaluated according to predefined rescue criteria as given below. All participants in the placebo group who meet rescue criteria at Week 16 will receive rescue treatment, i.e., guselkumab at Weeks 16, 20, and 24 followed by guselkumab 100 mg SC q8w. Participants randomized to guselkumab who meet rescue criteria at Week 16 will continue their assigned treatment regimen and receive blinded sham rescue with matching placebo SC injections at Weeks 16, 20, and 24.

Rescue criteria are defined as:

• No improvement (i.e., no decrease) in Mayo endoscopy subscore at Week 12, when compared with baseline

AND

• A <2 point improvement (i.e., <2 point decrease) in partial Mayo score at Weeks 12 and 16, when compared with baseline

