5.3.3.3. Missing at Random Multiple Imputation

Missing data for the primary estimand of the primary endpoint of clinical remission at Week 12 defined in Section 5.3.1 after the intercurrent event strategies have been applied will be summarized by intervention group. Data that is missing consists of data after discontinuation of study intervention for participants with ICEs in category 5 who do not have observed data at Week 12 and of missing data not related to ICEs.

This sensitivity analysis will evaluate the primary endpoint when all missing data as defined above are multiply imputed under the missing at random assumption. Imputation will be performed separately for all components of the primary endpoint. The following steps will be performed:

- 1. Any missing Mayo components pertaining to the primary endpoint at Week 12 will be imputed 500 times to generate 500 complete data sets using the fully conditional specification method, assuming missing at random. The following variables will be included in the imputation model: Mayo subscores at baseline and Week 12, partial Mayo subscores at Week 4 and Week 8, ADT-IR status and treatment group.
- 2. Each of the 500 resulting data sets will be analyzed using the common risk difference with Mantel-Haenszel weights, using baseline Mayo endoscopy subscore and ADT-IR status and as factors.
- 3. The results from the 500 data sets will be combined to produce inferential results based on Rubin's rules⁵⁾.

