5.4.2. Analysis Methods

5.4.2.1. Main Estimators (Analyses) for the Main Estimands for the Secondary Estimands

The analysis of the secondary endpoints will be based on the Full Analysis Set. Participants will be analyzed according to the treatment group to which they were randomized regardless of the treatment they received. After accounting for the ICE strategies, any missing data for the secondary endpoints will be handled by nonresponder imputation. In particular the following rules will be applied:

- Participants who are missing baseline stool frequency at baseline will be considered as not having achieved clinical remission or symptomatic remission at any timepoint
- Participants who are missing any of the modified Mayo subscores at baseline will be considered as not having achieved clinical response at any timepoint
- Participants who have missing endoscopy subscore at Week 12 will be considered as not having achieved endoscopic improvement or histologic-endoscopic mucosal improvement at Week 12;
- Participants who are missing either the stool frequency or the rectal bleeding subscore at Week 12 or at Week 24 will be considered as not having achieved symptomatic remission at the respective timepoint;
- Participants who are missing any of the modified Mayo subscores at Week 12 or at Week 24 will be considered as not having achieved clinical response at the respective timepoint;
- Participants who are missing any of the modified Mayo subscores at Week 24 will be considered as not having achieved clinical remission at Week 24;
- Participants who are missing any or all of the components in the Geboes grading system pertaining to the histologic improvement at Week 12 will be considered as not having achieved histologic-endoscopic mucosal improvement at Week 12.

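### When baseline stool frequency is missing, the SAP records non-remission even if the later subscore is 0, a value that cannot be an increase from any baseline

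*SAP*

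**What the plan says.** SAP 5.3.1 sets the endpoint: "Clinical remission is defined as a stool frequency subscore of 0 or 1 and not increased from baseline, a rectal bleeding subscore of 0", together with an endoscopy subscore of at most 1 without friability. The primary estimand (SAP 5.3.2.1) adds that no intercurrent event handled by the composite strategy has occurred before the visit. Symptomatic remission (SAP 5.4.1.1) uses the same stool frequency and bleeding conditions without the endoscopy.

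The main estimator then adds a rule on baseline data. For the primary endpoint, SAP 5.3.3.1 says: "Participants who are missing the stool frequency subscore at baseline will be considered not to be in clinical remission at Week 12". For the secondary endpoints, SAP 5.4.2.1 says: "Participants who are missing baseline stool frequency at baseline will be considered as not having achieved clinical remission or symptomatic remission at any timepoint". Neither sentence makes an exception for a post-baseline subscore of 0. Protocol 9.4.2.2 applies nonresponder imputation to missing Week 12 subscores and has no explicit rule for a missing baseline value.

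The SAP recognises the situation in one other place. Estimand 4 (SAP 5.3.2.2.3) narrows the population to participants who meet the entry criteria "and with a stool frequency subscore recorded at baseline". It is defined for the primary endpoint; the supplementary estimands for the secondary endpoints (SAP 5.4.1.3) have no counterpart.

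**The concern.** Nonresponder imputation is meant for outcomes that are unknown. Here, for one identifiable group, the outcome is known. If stool frequency at the visit is 0, it cannot have increased, so a missing baseline leaves nothing to impute. With bleeding 0, a qualifying endoscopy and no composite intercurrent event, the participant satisfies the estimand's variable, and the estimator still records failure. The estimator and the estimand it serves then disagree for that person.

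The stake is a known misclassification in the primary endpoint, which comes first in the testing sequence, and in other confirmatory endpoints built on the same condition. It would be corrected with data already collected.

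**Working it through.** **1. The logic.** The Mayo table is not visible in the public SAP. I take each subscore to run from 0 to 3, because the modified Mayo score has three components and a maximum of 9. Only the minimum of 0 matters for the main argument. Setting baseline 0, 1, 2, 3 against a later value of 0 or 1 gives eight pairs:

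- Later value 0: never an increase, from any of the four baselines.
- Later value 1: an increase only from baseline 0.

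So a later 0 is always determined. A later 1 without a baseline is not. Entry does allow baseline 0: stool frequency, bleeding and endoscopy of 0/2/3, 0/3/2 or 0/3/3 all reach a modified Mayo score of 5 or more.

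**2. Reach.** The fixed sequence (SAP 5.4.2.2) has 4 Week 12 tests, then 4 Week 24 endpoints for each of 2 regimens, then histologic-endoscopic mucosal improvement: 4 + 8 + 1 = 13. The rule touches clinical and symptomatic remission at Week 12 (2) and both at Week 24 for each regimen (4), so 6 of 13. Clinical response is outside this argument, because it needs a baseline modified Mayo score in any case.

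**3. The plan's own power.** Inputs from SAP 3: 8% against 22%, 133 against 266 participants, two-sided 0.05.

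- Pooled rate: (133 × 0.08 + 266 × 0.22) / 399 = 0.1733.
- Null standard error: √[0.1733 × 0.8267 × (1/133 + 1/266)] = 0.0402.
- Alternative standard error: √[0.08 × 0.92/133 + 0.22 × 0.78/266] = 0.0346.
- Power: Φ[(0.14 − 1.96 × 0.0402) / 0.0346] = 96.1%, in line with the stated figure of more than 95%.

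**4. Effect of the rule.** The documents give neither the share *m* with missing baseline stool frequency nor the share *q* of remitters whose later subscore is 0, so both are assumptions. I take *m* as equal across arms and unrelated to remission. Under the SAP rule, both rates are multiplied by (1 − *m*), so the difference is 14 × (1 − *m*) points. With an exception for a later 0, it is 14 × [1 − *m*(1 − *q*)] points.

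| *m* (assumed) | Participants of 399 | SAP rule: difference, power | With exception, *q* from 25% to 100% |
|---|---|---|---|
| 1% | about 4 | 13.86 points, 95.9% | 13.90 to 14.00 points, 96.0% to 96.1% |
| 2% | about 8 | 13.72 points, 95.7% | 13.79 to 14.00 points, 95.8% to 96.1% |
| 5% | about 20 | 13.30 points, 95.0% | 13.48 to 14.00 points, 95.3% to 96.1% |

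The full loss is 14.00 − 13.86 = 0.14 points at 1% and 14.00 − 13.30 = 0.70 points at 5%. These are upper bounds on what the exception recovers, reached only if every affected remitter has a later subscore of 0.

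**5. One case in the observed data.** A wrongly scored guselkumab remitter moves the unadjusted difference by 1/266 = 0.38 points, downwards. A wrongly scored placebo remitter moves it by 1/133 = 0.75 points, upwards.

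**The case against.** The strongest reply is that the group is nearly empty. Entry requires active disease "defined as a modified Mayo score of 5 to 9, inclusive", stool frequency is part of that score, the protocol allows no waivers, and diaries cover the 10 days before Week 0. Without stool frequency, only bleeding plus endoscopy of 5 or 6 could establish eligibility. This stands, and it is why the point is minor.

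A second reply is that the rule extends a uniform, pre-specified and conservative convention. That is fair for a later subscore of 1, where the status is unknown. It does not cover a later 0, where nothing is unknown. The conservatism also depends on similar missingness across arms.

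A third reply is that the plan already mitigates. Estimand 4 restricts on a pre-treatment variable, keeps a randomised comparison and removes the misclassification from that analysis. It does so by exclusion and for the primary endpoint only. The tipping-point analysis (SAP 5.3.3.3.1) varies the status of participants with missing primary endpoint data, and it can be read as including these cases. The multiple imputation analysis has baseline Mayo subscores in its model, but what it undertakes to fill in is: "Any missing Mayo components pertaining to the primary endpoint at Week 12 will be imputed 500 times". Neither analysis says how a missing baseline value is treated.

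Finally, the Mayo scoring details are not visible in the public copy. Whatever leaves the baseline value missing might also leave later values missing, which would shrink the group further.

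**Conclusion.** The point holds as a small inconsistency between estimator and estimand. For a post-baseline stool frequency of 0, the rule records failure where the observed data meet the definition, in 6 of 13 confirmatory tests. The conclusion rests on a scale minimum of 0. Its size rests on assumed missingness: for 1% to 5%, equal across arms, up to about 0.1 to 0.7 points on the expected risk difference and at most about 1 point of power.

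Three stronger readings are tempting and are not supported:

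- **That Estimand 4 shows such cases are expected.** It may be purely precautionary, and the documents report no count.
- **That the rule necessarily biases the effect towards zero.** This holds in expectation if missingness is similar across arms. With a handful of cases, chance imbalance could push the observed difference either way.
- **That every affected participant who otherwise qualifies is misclassified.** With a later subscore of 1 the no-increase condition is undetermined, so non-response is defensible.

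**What to change.** In SAP 5.3.3.1 and 5.4.2.1, add: when the baseline stool frequency subscore is missing, the no-increase criterion counts as met at any visit where the stool frequency subscore is 0; where it is 1, the participant remains a non-responder. Report by arm how many participants are affected.

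The cost is one sentence in two places and a matching change to the responder derivation, with no new data. Timing matters. The sponsor is unblinded at the Week 24 database lock (Protocol 6.3), and the documents do not show whether that lock has taken place. If it has, leave the primary derivation unchanged and report the re-scored result as a supplementary analysis.
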